
Data Analysis:
 
The core population (CP) is defined as all patients of the target population (TP) (definition see above), who have started the treatment combination recommended in the current local label for their disease characteristics. Patients not receiving the treatment recommended in the local label will be summarized in the non-core population (NCP). In addition, the core population with sufficient follow-up data (CPSFU) is defined as all CP patients, who have (i) evaluable HCV RNA data \geq70 days after the last actual dose of the ABBVIE REGIMEN or (ii) a HCV RNA value \geq50 IU/mL at the last measurement or (iii) had HCV RNA $<$50 IU/mL at the last measurement, but no HCV RNA measurement \geq70 days after the last actual dose of the ABBVIE REGIMEN due to reasons related to safety (e.g. dropped out due to adverse event) or incomplete efficacy information (e.g. virologic failure such as relapse is reported in the electronic case report form (eCRF) but date and value of the corresponding HCV RNA test is missing). The safety population (SP) is defined as all patients who received at least one dose of the ABBVIE REGIMEN.
 
Descriptive and exploratory statistical methods will be used to analyze the data of the study. All baseline and disease characteristics will be summarized for the CP stratified by the CP analysis groups (based on genotype 1 subtype, fibrosis status, treatment experienced or naïve), which are relevant for scheduled treatment combination (\pm dasabuvir, \pm RBV) and duration (12 or 24 weeks). In addition, baseline summaries will be repeated for the SP and TP without stratification into subgroups. Further details of analysis populations and the CP analysis groups will be specified in the statistical analysis plan (SAP).
 
The primary effectiveness analysis will be performed for CP patients, stratified by the CP

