AbbVie's interferon-free regimen for the treatment of CHC includes 3 DAAs targeting different steps in HCV replication. Paritaprevir (ABT-450) is a NS3/4A protease inhibitor with nanomolar potency *in vitro* and is co-administered with low-dose ritonavir, an inhibitor of the cytochrome P-450 enzyme CYP3A4. As a pharmacologic enhancer of paritaprevir, ritonavir co-administration with paritaprevir (paritaprevir/r) results in higher drug exposures than administration of paritaprevir alone [55]. Ombitasvir (ABT-267) is a nonstructural protein 5A (NS5A) inhibitor with picomolar potency *in vitro*, and dasabuvir (ABT-333) is a NS5B non-nucleoside polymerase inhibitor with nanomolar potency *in vitro*.

The 3 DAA combination of paritaprevir/r – ombitasvir plus dasabuvir with or without RBV has been initially evaluated in 6 Phase III studies with genotype 1 infected patients (SAPPHIRE-I [56], SAPPHIRE-II [57], PEARL-II [58], PEARL-III [59], PEARL-IV [59], TURQUOISE-II [60]).

Therapy for 12 weeks with the above regimen in non-cirrhotic patients resulted in the following SVR rates 12 weeks after EoT (SVR12):

Table 1 - SVR12 rates in clinical trials:

Population and treatment duration	Genotype	SVR12 ABBVIE REGIMEN + RBV	SVR12 ABBVIE REGIMEN alone
Non-cirrhotic, treatment-naïve (12 weeks)	1a	95-97% (SAPPHIRE-I, PEARL-IV)	90% (PEARL-IV)
	1b	98-99.5% (SAPPHIRE-I, PEARL-III)	99% (PEARL-III)
Non-cirrhotic, treatment-experienced (12 weeks)	1a	96% (SAPPHIRE-II)	n.a.
	1b	97% (SAPPHIRE-II, PEARL-II)	100% (PEARL-II)

These results suggest that the ABBVIE REGIMEN with RBV is the optimal regimen for genotype 1a infected patients, while patients with genotype 1b do not require RBV.

The TURQUOISE-II [60] study explored the efficacy of the ABBVIE REGIMEN in the traditionally most difficult-to-treat cirrhotic patients. This large study enrolled exclusively genotype 1 infected patients with cirrhosis, including treatment-naïve and treatment-experienced individuals. All patients received the ABBVIE REGIMEN with RBV and were

Confidential Information

No use or disclose outside AbbVie is permitted without prior written authorization from AbbVie

Version 3.0 (22 Apr 2015) – country v 1.0 dated 26.06.2015

Page 17 of 61

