randomized to 12 or 24 weeks of therapy. Overall 92% and 96% of patients achieved SVR following treatment for 12 or 24 weeks, respectively. Analysis of subgroups demonstrated that the small difference in SVR between treatment arms was due largely to the subgroup of genotype 1a treatment-experienced prior null responders treated for 12 weeks who achieved an SVR of 80%. This subgroup of patients achieved an SVR of 93% when treated for 24 weeks. Among genotype 1a infected patients, partial responders and relapsers had higher SVR rates than null responders in the 12 week treatment group, while similar SVR rates were seen among the null responders, partial responders and relapsers treated for 24 weeks, suggesting that the longer duration of 24 weeks is required only for cirrhotic genotype 1a null responders. SVR rates were very high across all subgroups in genotype 1b treatment-experienced patients treated for 12 and 24 weeks.

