9.7.3 Effectiveness Analysis

The primary effectiveness analysis on clinical outcomes will be performed on all patients in the CP stratified by the CP analysis groups. Due to the non-interventional nature of this study several different methods for determination of the HCV RNA value can be applied. For the purpose of the statistical analysis, a HCV RNA measurement is considered ≤ 50 IU/mL,

- if a PCR test was used
- and the test result is undetectable and the LLoD of the test is ≤ 50 IU/mL or the test result is unquantifiable and the LLoQ is ≤ 50 IU/mL

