9.7.3.3 Statistical Methods for Analysis of Effectiveness Variables

The simple percentage of patients achieving SVR12 will be calculated and an exact two-sided 95% confidence interval (CI) of the percentage will be computed based on the Clopper-Pearson method.

Corresponding methods will be used for other response rates (EoT response rate, relapse rate, viral breakthrough). The relapse rates will be estimated in patients of the CP analysis groups with EoT response and sufficient HCV RNA measurements post-

treatment. Viral breakthrough rates will be estimated in all patients of the CP analysis groups, who have at least one undetectable HCV RNA measurement on-treatment and at least one on-treatment or EoT measurement thereafter.

Univariate and multiple logistic regression (MLR) methods will be used to investigate the impact of the following explanatory covariates on SVR12:

- Key demographic information
- Mode of CHC infection
- HCV RNA level at baseline
- Most recent stage of liver fibrosis
- HCV genotype and subtype (if available)
- Type of treating institute
- Liver and/or CHC related co-morbidities
- Key clinical chemistry and hematology laboratory variables at baseline
- In treatment experienced patients only:
 - Most recent prior treatment for CHC
 - Outcome of most recent prior CHC treatment

Further details and additional covariates will be specified in the SAP.

These analyses will be of exploratory nature, data driven, and will be repeatedly performed for various CP Analysis Groups, since not each covariate might be predictive in each patient group. Furthermore, the fact that treatment regimens will differ in the various patient groups has to be taken into account, when selecting the patient groups for each MLR analysis. Backward selection procedures will be applied to generate the final MLR models which consider only covariates in the selection procedure with a p-value <0.25 in the corresponding univariate logistic regression analysis. A p-value <0.05 will be used for the covariates to stay in the model in a backward elimination step. Logistic regression methods will also be used to investigate the impact of treatment adherence on SVR12.

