Annex 5. Child-Pugh Classification of Severity of Cirrhosis

Parameter	Points Assigned for Observed Findings		
	1	2	3
Total bilirubin, $\mu\text{mol/L}$ (mg/dL)	<34.2 (<2)	34.2 – 51.3 (2 – 3)	>51.3 (>3)
Serum albumin, g/L (g/dL)	>35 (>3.5)	28 – 35 (2.8 – 3.5)	<28 (<2.8)
INR	<1.7	1.7 – 2.3	>2.3
Ascites*	None	Slight	Moderate to severe
Hepatic encephalopathy**	None	Grade 1 or 2 (or suppressed with medication)	Grade 3 or 4 (or refractory)

* None.

Slight ascites = Ascites detectable only by ultrasound examination.

Moderate ascites = Ascites manifested by moderate symmetrical distension of the abdomen.

Severe ascites = Large or gross ascites with marked abdominal distension.

** Grade 0: normal consciousness, personality, neurological examination, electroencephalogram.

Grade 1: restless, sleep disturbed, irritable/agitated, tremor, impaired handwriting, 5 cps waves.

Grade 2: lethargic, time-disoriented, inappropriate behavior, asterixis, ataxia, slow triphasic waves.

Grade 3: somnolent, stuporous, place-disoriented, hyperactive reflexes, rigidity, slower waves.

Grade 4: unarousable coma, no personality/behavior, decerebrate, slow 2 to 3 cps delta activity

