## 9 Effectiveness analysis

Effectiveness analysis will be conducted on *the core population (CP)*, *the target population (TP)* and *the core population with sufficient follow-up data (CPSFU)*.

The results will be reported overall and for scheduled treatment combination ( $\pm$  RBV) and duration (12 or 24 weeks) groups. Additionally and only for *the core population (CP)* the results will be presented for the CP analysis groups by the following parameters:

- HCV genotype and subtype (1a or 1b);
- fibrosis status (the Child Pugh Score class: A, B or C);
- treatment experienced or naïve patients (with/without prior treatment for CHC).

Tables with descriptive statistics will be prepared in accordance with section 7.1. Confidence intervals will be presented according the section 7.2. All corresponding listings will be presented. Additional listings for *the non-core population (NCP)* will be created.

The following effectiveness endpoints will be analyzed:

- the percentage of patients achieving SVR12 (single last HCV RNA <50 IU/mL 12 weeks after the last actual dose of the ABBVIE REGIMEN);
- the percentage of patients with at least one and each of SVR12 non-response categories:
  - breakthrough (at least one documented HCV RNA <50 IU/mL followed by HCV RNA  $\geq$ 50 IU/mL during treatment);
  - failure to suppress (each measured on-treatment HCV RNA value  $\geq$ 50 IU/mL);

---

 Parameter “HCV Genotype and Subtype” from eCRF form “CHC DISEASE CHARACTERISTICS”.

 Parameter “Class” in section “Child Pugh Score” from eCRF form “Liver fibrosis stage”.

 Parameter “Prior treatment for CHC?” from eCRF form “MOST RECENT PRIOR THERAPY FOR CHC”.

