**Table 2.2.1.2. SVR12 achieving response. Multiple logistic regression results**  
The core population  
Page X of X

| Patients for analysis (n) |                       | Overall               |
|---------------------------|-----------------------|-----------------------|
| [Predictor name]          |                       | XXX                   |
| OR (95% Wald CI)          | X.XXX (X.XXX - X.XXX) |                       |
| p-value                   | 0.XXXX                |                       |
| [Predictor name]          |                       | X.XXX (X.XXX - X.XXX) |
| OR (95% Wald CI)          |                       | 0.XXXX                |
| p-value                   |                       | ...                   |

SVR12: sustained virological response at 12 weeks after EoT.  
Table for the core population with sufficient follow-up data is the same table for the core population because the core population and the The core population with sufficient follow-up data are equal (contain exactly the same subjects).

Program code, date, time Data extracted: DD.MM.YYYY

Similar to tables 2.2.1.1-2.2.1.2, tables 2.2.X.X for the following subgroups will be constructed:

- with/without Ribavirin;
- Child Pugh class A/B/C;
- with/without treatment experienced.

Similar to tables 2.2.X.X, tables 2.3.X.X for the target population and tables 2.4.X.X for the core population with sufficient follow-up data will be constructed.

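### SAP 8 and 9 define fibrosis status as Child-Pugh class A/B/C, so the planned strata have no non-cirrhotic level and give no cirrhotic versus non-cirrhotic SVR12 rate

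*SAP*

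**What the plan says.** Protocol 9.7.3 performs the primary effectiveness analysis in the CP, "stratified by the CP analysis groups". The abstract and 9.7.2 say these groups are "based on genotype 1 subtype, fibrosis status" and prior-treatment status, and leave further detail to the SAP. Fibrosis status is not defined further there. Section 9.7.3.3 lists a staging variable, "Most recent stage of liver fibrosis", among the regression covariates.

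SAP 8 (baseline summaries) and SAP 9 (effectiveness) both set the fibrosis factor to "the Child Pugh Score class: A, B or C". A footnote ties it to the Class field of the Child-Pugh section on the eCRF liver fibrosis form. The note under Table 2.2.1.2 repeats the SVR12 regressions by "Child Pugh class A/B/C".

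The protocol annex titles the score "Child-Pugh Classification of Severity of Cirrhosis", and the covariate list in SAP 9 describes it in the same sense. The class rows of shell Table 1.6.1 are A, B and C only, and the footnotes to the subgroup shells divide patients into the same three classes.

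SAP 6 excludes from the CP patients whose fibrosis status is unknown, and a further subset identified by being cirrhotic. It does not say which variable decides either. SAP 16 declares the methods consistent with the protocol and mentions only the dropped patient-support-program regression.

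**The concern.** Child-Pugh grades how severe a cirrhosis is. It does not record whether a patient has cirrhosis, or how far fibrosis has progressed short of it. Used as the fibrosis stratum, it leaves no level for non-cirrhotic patients.

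The documents themselves rely on the missing split. Protocol 7.1 introduces its main reference SVR12 rates with "Therapy for 12 weeks with the above regimen in non-cirrhotic patients", and gives the results of the cirrhosis trial separately: "Overall 92% and 96% of patients achieved SVR following treatment for 12 or 24 weeks". SAP 6 also treats cirrhotic patients as an identifiable subset of the CP. A reader who wants the real-world SVR12 rate in non-cirrhotic patients, or a comparison with cirrhotic patients, would not find either in the planned stratified output.

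**Working it through.** **1. The plan's own figure.** Inputs: n = 158 and SVR12 90% (Protocol 9.5, SAP 4.2). The exact limits are the 2.5% quantile of Beta(x, n-x+1) and the 97.5% quantile of Beta(x+1, n-x). With x = 158 × 0.9 = 142.2 the interval is 84.23 to 94.20, width 9.97 points. This reproduces the stated 84.2-94.2 and 10.0%. The figure concerns the overall CP and does not depend on the strata.

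**2. Where each patient goes under the SAP rule.** The eCRF is not supplied, so both ways of recording the class have to be followed.

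- *(a) Class recorded only in cirrhosis.* Classes A, B and C are the cirrhotic patients, and their SVR12 is reported by class. Non-cirrhotic patients appear in no fibrosis stratum. Subtracting the three classes from the overall row gives only an approximation, because cirrhotic patients with a missing class fall into the remainder.
- *(b) Class recorded for everyone.* The annex scores five parameters at 1 to 3 points, so a patient normal on all five scores 5 × 1 = 5, the minimum. A compensated cirrhotic patient can score the same. Both sit in the lowest class, A, and cannot be separated.

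Neither case yields a non-cirrhotic rate or a cirrhotic versus non-cirrhotic split.

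**3. Illustrative size.** The documents give no shares. Assumptions: 50-80% of the 158 non-cirrhotic; 0-20% of cirrhotic patients with a missing class in case (a); 0-20% in class B or C in case (b).

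| Quantity | 50% non-cirrhotic | 80% non-cirrhotic |
|---|---|---|
| Non-cirrhotic / cirrhotic | 158 × 0.5 = 79 / 79 | 158 × 0.8 = 126 / 32 |
| (a) In no fibrosis stratum, before missing classes | 79 | 126 |
| (a) Cirrhotic patients in the remainder at 20% missing | 79 × 0.2 = 16; 16/95 = 17% | 32 × 0.2 = 6; 6/132 = 5% |
| (b) Class A at 20% in B or C | 79 + 79 × 0.8 = 142 (90%) | 126 + 32 × 0.8 = 152 (96%) |
| (b) Class A at 0% in B or C | 158 (100%) | 158 (100%) |

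**4. Does any other output fill the gap?** The regression covariates in SAP 9 include FibroTest and five histology scores, but not FibroScan. The shell for those models (Table 2.2.1.1.1) shows n, odds ratio with Wald interval, and p-value, so no stratum rate is printed. The SVR12 percentage shells (2.1.x) have treatment columns, and the follow-on list adds other populations and definitions but no version by CP analysis group. The text of SAP 9 promises those results, so that text is the only rule for the SVR12 strata.

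**5. What a corrected split could deliver.** At 90% SVR12 in both strata, with the same formula, an even split (79 and 79) gives intervals 14.4 points wide. A split of 32 cirrhotic and 126 non-cirrhotic gives 23.6 and 11.2. The 10-point target was set for the overall CP only.

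**The case against.** *The definition was the SAP's to make.* The supplied protocol does not define fibrosis status and hands the group details to the SAP. It is also version 3.0, whereas SAP 2 cites version 4.0 of 11 July 2017, which is not supplied. This stands to the extent that a departure from the governing protocol cannot be shown. What remains is visible within the SAP: a factor labelled fibrosis status is filled by a variable the SAP itself calls severity of cirrhosis.

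*Fibrosis and cirrhosis are not absent from the SVR12 results.* In case (a) cirrhotic patients' SVR12 is printed by class, biopsy scores and FibroTest may enter the regressions, and endpoint listings are planned. All true. But the regressions are optional and exploratory and give odds ratios, and listings are not summaries. No planned table gives the non-cirrhotic rate.

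*The comparison with the reference rates is not an objective, and a one-way split would not match them.* The rates in Protocol Table 1 are broken down by subtype, prior treatment and ribavirin use, so a cirrhosis stratum alone gives context, not a like-for-like comparison. This stands and limits the benefit.

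*The shares are assumed.* Correct. The ranges illustrate scale. The conclusion rests on the levels of the variable, not on the shares.

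**Conclusion.** The rule is wrong as written and should be changed. Confidence is moderate to high, with the unseen protocol version 4.0 and the unseen eCRF as the main reservations. Under either way of recording the class, the planned strata give no SVR12 rate for non-cirrhotic patients and no cirrhotic versus non-cirrhotic split. The affected outputs are descriptive strata and exploratory regressions. The overall SVR12 estimate and N=158 are unaffected.

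Two stronger readings are tempting and not supported.

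- A reader might infer that patients without a Child-Pugh class count as having unknown fibrosis status under SAP 6, so that non-cirrhotic patients leave the CP and the overall interval widens. SAP 6 carries no Child-Pugh footnote; that mapping is given only for the reporting groups. Its next exclusion singles out cirrhotic patients, a word that would be redundant if only they remained. What can be said is that SAP 6 gives no derivation for either term. No loss of CP patients should be claimed.
- A reader might infer that SVR12 is not related to fibrosis or cirrhosis anywhere in the output. The printed cirrhotic classes in case (a) and the staging covariates in the regressions show otherwise.

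**What to change.** Define one variable with levels non-cirrhotic, cirrhotic and unknown. Take it from a direct cirrhosis item on the eCRF if there is one. Otherwise derive it from the staging data already collected: biopsy score, FibroScan, FibroTest and clinical judgement (SAP 8.4, Table 1.6.1). Fix the order of methods and the cirrhosis cut-offs before database soft lock, the point up to which SAP 2 allows revision, and show the method used for each patient. A simple latest-assessment rule is not advisable. The baseline list and shell show no dates by method, and such a rule would let a later best guess override a biopsy.

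Use the variable as the fibrosis stratum in SAP 8 and 9, for the regression subgroups, and for the two SAP 6 filters that now lack a derivation. Keep Child-Pugh class as a sub-split of cirrhotic patients. Add the SVR12 percentage shells by this stratum that SAP 9 already promises, and record the definition in SAP 16.

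The cost is SAP and shell wording plus one derived variable, with no new data expected as long as the staging fields are filled. Mapping different methods to one threshold will leave some misclassification, and clinical staging is the least certain source. The strata will also be less precise than the overall estimate.

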9.7.3.2 Secondary Effectiveness Endpoints

The secondary effectiveness endpoints are:

- The percentage of patients with virological response (HCV RNA <50 IU/mL) at EoT
- The percentage of patients with relapse (defined as HCV RNA <50 IU/mL at EoT followed by HCV RNA ≥50 IU/mL)
- The percentage of patients with breakthrough (defined as at least one documented HCV RNA <50 IU/mL followed by HCV RNA ≥50 IU/mL during treatment).
- The number and percentage of patients meeting each and any of the following SVR12 non-response categories:
 - On-treatment virologic failure (breakthrough [defined as above] or failure to suppress [each measured on-treatment HCV RNA value ≥50 IU/mL])
 - Relapse (defined as HCV RNA <50 IU/mL at EoT or at the last on-treatment HCV RNA measurement followed by HCV RNA ≥50 IU/mL post-treatment)
 - Premature study drug discontinuation with no on-treatment virologic failure
 - Missing SVR12 data and/or none of the above criteria

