### 3.2.2 Secondary variables

- effectiveness endpoints:
  - the percentage of patients with virological response (HCV RNA <50 IU/mL) at EoT;
  - the percentage of patients with relapse (defined as HCV RNA <50 IU/mL at EoT followed by HCV RNA  $\geq 50$  IU/mL);
  - the percentage of patients with breakthrough (defined as at least one documented HCV RNA <50 IU/mL followed by HCV RNA  $\geq 50$  IU/mL during treatment);
  - the number and percentage of patients meeting each and any of the following SVR12 non-response categories:
    - on-treatment virologic failure: breakthrough (defined as above) or failure to suppress (each measured on-treatment HCV RNA value  $\geq 50$  IU/mL);
    - relapse (defined as HCV RNA <50 IU/mL at EoT or at the last on-treatment HCV RNA measurement followed by HCV RNA  $\geq 50$  IU/mL post-treatment);
    - premature study drug discontinuation with no on-treatment virologic failure;
    - missing SVR12 data and/or none of the above criteria;
- co-morbidities and concomitant medication;
- serious and non-serious adverse events and pregnancy occurrences;
- questionnaires on PROs: EQ-5D-5L questionnaire and WPAI questionnaires prior to treatment initiation at EoT as well as SVR12 and SVR24 (12 and 24 weeks after EoT respectively);
- Patient Activate Measure 13 (PAM-13), patient support program (PSP) satisfaction and utilization questionnaires.

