**P15-743 (HCV RWE) \_ STATISTICAL ANALYSIS PLAN \_ Final 2.0 \_ 02 Feb 2018**

---

- relapse (HCV RNA <50 IU/mL at EoT or at the last on-treatment HCV RNA measurement followed by HCV RNA  $\geq$ 50 IU/mL post-treatment);
- premature study drug discontinuation with no on-treatment virologic failure;
- missing SVR12 data;
- the percentage of patients achieving SVR24 (single last HCV RNA <50 IU/mL 24 weeks after the last actual dose of the ABBVIE REGIMEN);
- the percentage of patients with virological response (HCV RNA <50 IU/mL) at EoT.

Due to the fact that in the Russian clinical practice tests for HCV RNA often have limit of detection higher than 50 IU/mL (for example, 60 or 100 IU/mL), additional analysis will be performed. In this case all above mentioned effectiveness endpoints will be analyzed with the following definitions:

- the percentage of patients achieving SVR12 (single last HCV RNA value <50 IU/mL or undetectable/negative 12 weeks after the last actual dose of the ABBVIE REGIMEN);
- the percentage of patients with at least one and each of SVR12 non-response categories:
  - breakthrough (at least one documented HCV RNA value <50 IU/mL or undetectable/negative followed by HCV RNA value  $\geq$ 50 IU/mL or positive during treatment);
  - failure to suppress (each measured on-treatment HCV RNA value  $\geq$ 50 IU/mL or positive);
  - relapse (HCV RNA value <50 IU/mL or undetectable/negative at EoT or at the last on-treatment HCV RNA measurement followed by HCV RNA  $\geq$ 50 IU/mL or positive post-treatment);
  - premature study drug discontinuation with no on-treatment virologic failure;
  - missing SVR12 data and/or none of the above criteria;
- the percentage of patients achieving SVR24 (single last HCV RNA value <50 IU/mL or undetectable/negative 24 weeks after the last actual dose of the ABBVIE REGIMEN);
- the percentage of patients with virological response (HCV RNA value <50 IU/mL or undetectable/negative) at EoT.

Achieving SVR12 and presence of breakthrough, relapse or failure to suppress as well as virological response at EoT will be analyzed using univariate logistic regression for both cases (main and sensitivity analyses). These analyses will be of exploratory nature, data driven, and will be repeatedly performed for various CP analysis groups, since not each covariate might be predictive in each patient group. The following parameters can be included in the univariate models as explanatory variables (fixed effect or covariate):

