**Table 2.1.1.1.1. Percentage for effectiveness endpoints (main analysis)**  
The core population  
Page X of X

| Parameter   | ABBVIE REGIMEN + RBV                  |  | ABBVIE REGIMEN - RBV                  |     | Overall
(N=XXX)
n (%)
95% CI |
|---|---------------------------------------|--|---------------------------------------|-----|---------------------------------------|
|   | 12 weeks
(N=XX)
n (%)
95% CI |  | 12 weeks
(N=XX)
n (%)
95% CI |     |                                       |
| Patients achieving SVR12
(single last HCV RNA <50 IU/mL 12 weeks after the last actual dose
of the ABBVIE REGIMEN)                            | XX (XX.X)
(XX.X - XX.X)            |  | XX (XX.X)
(XX.X - XX.X)            | ... | XX (XX.X)
(XX.X - XX.X)            |
| SVR12 non-response  | XX (XX.X)
(XX.X - XX.X)            |  | XX (XX.X)
(XX.X - XX.X)            | ... | XX (XX.X)
(XX.X - XX.X)            |
| Patients with breakthrough
(defined as at least one documented HCV RNA <50 IU/mL
followed by HCV RNA ≥50 IU/mL during treatment)              | XX (XX.X)
(XX.X - XX.X)            |  | XX (XX.X)
(XX.X - XX.X)            | ... | XX (XX.X)
(XX.X - XX.X)            |
| Failure to suppress
(each measured on-treatment HCV RNA value ≥50 IU/mL)   | XX (XX.X)
(XX.X - XX.X)            |  | XX (XX.X)
(XX.X - XX.X)            | ... | XX (XX.X)
(XX.X - XX.X)            |
| Patients with relapse
(HCV RNA <50 IU/mL at EoT or at the last on-treatment HCV RNA
measurement followed by HCV RNA ≥50 IU/mL post-treatment) | XX (XX.X)
(XX.X - XX.X)            |  | XX (XX.X)
(XX.X - XX.X)            | ... | XX (XX.X)
(XX.X - XX.X)            |
| Patients with missing SVR12 data  | XX (XX.X)
(XX.X - XX.X)            |  | XX (XX.X)
(XX.X - XX.X)            | ... | XX (XX.X)
(XX.X - XX.X)            |
| Patients with premature study drug discontinuation with
no on-treatment virological failure  | XX (XX.X)
(XX.X - XX.X)            |  | XX (XX.X)
(XX.X - XX.X)            | ... | XX (XX.X)
(XX.X - XX.X)            |
| Patients achieving SVR24
(single last HCV RNA <50 IU/mL 24 weeks after the last
actual dose of the ABBVIE REGIMEN)                            | XX (XX.X)
(XX.X - XX.X)            |  | XX (XX.X)
(XX.X - XX.X)            | ... | XX (XX.X)
(XX.X - XX.X)            |

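### The SAP main analysis drops the residual SVR12 non-response category and never ties the categories to SVR12 failure, so SVR12 plus non-response need not total 100%

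*SAP*

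**What the plan says.** SAP 9 lists the effectiveness endpoints. After SVR12 comes "the percentage of patients with at least one and each of SVR12 non-response categories". For the main analysis the categories are:

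- "breakthrough (at least one documented HCV RNA <50 IU/mL followed by HCV RNA" at or above 50 IU/mL during treatment;
- "failure to suppress (each measured on-treatment HCV RNA value" at or above 50 IU/mL;
- "relapse (HCV RNA <50 IU/mL at EoT or at the last on-treatment HCV RNA measurement followed by HCV RNA" at or above 50 IU/mL after treatment;
- "premature study drug discontinuation with no on-treatment virologic failure";
- missing SVR12 data, with nothing further.

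Shell 2.1.1.1.1 follows this list. It has an SVR12 non-response summary row with n, percentage and confidence interval out of all core-population patients, and its missing-data row reads "Patients with missing SVR12 data". Shell 2.1.1.1.3 repeats the table without patients whose SVR12 result is missing, and so has neither a missing-data row nor a residual row.

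Elsewhere the list closes differently. Protocol 9.7.3.2 ends with "Missing SVR12 data and/or none of the above criteria". SAP 3.2.2 ends with "missing SVR12 data and/or none of the above criteria", and the additional analysis in SAP 9 ends with the same words. SAP 16 states that the methods agree fully with the protocol and names only one exception, the dropped regression for the patient support program.

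**The concern.** This breakdown is where a reader will look to learn why patients did not reach the primary endpoint. For that purpose it has to account for every patient without SVR12 and for nobody else. As written it does neither with certainty. Without the residual category some patients without SVR12 have no row. And because a patient enters the summary row by meeting at least one category, while no category mentions the SVR12 result, a patient who achieved SVR12 can enter it too. The two errors work in opposite directions and could partly cancel, so the total alone would not reveal them. At stake is the agreement of a secondary table with the primary result, not the primary result itself.

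**Working it through.** **Context figure.** The plan's precision statement reproduces. With 142.2 of 158 responders (90%), the Clopper-Pearson 95% interval is 84.23% to 94.20%, width 9.97, against the stated 84.2 to 94.2 and 10.0. Nothing below changes this.

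**Step 1. Closing category, side by side.**

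| Place | Residual category present? |
|---|---|
| Protocol 9.7.3.2 | Yes |
| SAP 3.2.2 | Yes |
| SAP 9, additional analysis | Yes |
| SAP 9, main analysis | No |
| Shell 2.1.1.1.1 | No |
| Shell 2.1.1.1.3 | No, and no missing-data row |

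**Step 2. Who has no row.** Protocol 9.7.3 accepts an undetectable result as response only if the assay's lower limit of detection (LLoD) is at most 50 IU/mL. SAP 9 says Russian assays often have a higher limit, such as 60 or 100. HCV RNA testing is at the physician's discretion (Protocol 9.7.1), and SAP 7.3 imputes nothing. Two kinds of patient without SVR12 then fall outside the main list:

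- The SVR12 result exists but cannot be placed against 50 IU/mL, for example undetectable with LLoD 100. It is not accepted as below 50, not shown to be at or above 50, and not missing. A qualitative positive with no value is in the same position, because positive results are mentioned only in the additional definitions.
- The SVR12 result is at or above 50 IU/mL, but no on-treatment or end-of-treatment result can be placed against 50. Relapse and breakthrough need a documented value below 50; failure to suppress needs measured values at or above 50.

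**Step 3. Which achievers can be counted.** Read literally:

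- a patient with a transient on-treatment value at or above 50 after one below 50 meets breakthrough, whatever happens later;
- a patient whose only on-treatment test was early and at or above 50 meets failure to suppress;
- a patient who stops early without on-treatment virologic failure and then achieves SVR12 meets the discontinuation category. SAP 6 keeps those who stop by day 55 (12-week course) or day 139 (24-week course) in the target population, where effectiveness is also analysed;
- under the SAP 5.2 window (days 57 to 112 after the last dose), a patient below 50 at SVR12 and at or above 50 at week 24 meets relapse, which has no time limit.

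**Step 4. Enumeration.** The main definitions were applied literally to every combination of 0 to 3 on-treatment results; early post-treatment, SVR12 and SVR24 results; and early stop yes or no. End of treatment was taken as the last on-treatment result. These are counts of possible patterns, not patient frequencies.

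- Results only below 50 or at/above 50: (1+2+4+8) × 3³ × 2 = 810 patterns. In 237, an SVR12 achiever meets at least one category. In 9, a patient with SVR12 at or above 50 meets none; all 9 lack any on-treatment result.
- Adding results that cannot be placed: (1+3+9+27) × 4³ × 2 = 5,120 patterns. In 900, an achiever meets a category. In 652, a non-achiever meets none: 380 with an unplaceable SVR12 result and 272 with SVR12 at or above 50.

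**Step 5. Size.** One patient is 1/158 = 0.63 points. The complement of SVR12 is 16/158 = 10.1% if 142 achieve it, and 8/158 = 5.1% if 150 do. As an assumption, let 0 to 5% of achievers also meet a category (0 to 7 of 142, or 0 to 8 of 150) and 0 to 5% of all patients have no category (0 to 8 of 158):

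- 142 achievers: the row runs from 16 − 8 = 8 (5.1%) to 16 + 7 = 23 (14.6%);
- 150 achievers: from 8 − 8 = 0 (0.0%) to 8 + 8 = 16 (10.1%).

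SVR12 plus the row then totals between 94.9% (150/158) and 105.1% (166/158).

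**The case against.** The label itself speaks of SVR12 non-response, and the shell puts the summary row directly beneath the SVR12 row, so a programmer may well limit the categories to patients without SVR12. That is a fair reading. A reader might infer that the plan will report cured patients as failures; the documents do not show this. They leave the question open.

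The early-stopper example is also weaker in the core population. SAP 6 uses the language of premature discontinuation for stops by day 55 or day 139 and excludes those patients from the core population. Neither document says whether a day-70 stop of a 12-week course is premature. The example is certain only in the target population.

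A reader might further infer that this defect lowers the SVR12 rate. It does not. If 16 of 158 patients (an assumed 10.1%) were undetectable on an assay with LLoD above 50, the main SVR12 rate would fall because of the detection-limit rule in Protocol 9.7.3, and would fall equally with a complete list. Nor is such a patient shown to be a true failure.

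The additional analysis counts undetectable results as response, keeps the residual category and sits beside the main table, and listings are planned, so these patients are traceable. SAP 7.1 replaces quantitative values below the limit of quantification by half that limit, which might place some results. But that rule is written for descriptive statistics and cannot place a qualitative result.

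Where at least one on-treatment result exists and all results can be placed against 50 IU/mL, no observed failure is left out.

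Finally, the SAP cites protocol version 4.0, while the protocol supplied is version 3.0. The conflict between SAP 3.2.2 and SAP 9 stands regardless.

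**Conclusion.** The point holds in two parts of different strength. The missing residual category is a plain inconsistency: the main analysis and its shells differ from SAP 3.2.2, from the additional analysis and from the supplied protocol, and SAP 16 does not declare it. The lack of any link to SVR12 failure is an ambiguity, inherited from the protocol wording, that the SAP should close; it is not a demonstrated miscount.

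The consequence is that SVR12 and SVR12 non-response need not sum to 100% in the secondary breakdown. The fault is clearest in shell 2.1.1.1.3, where missing results have already been removed. The size is 0.63 points per patient at N = 158; how many patients are affected cannot be derived from the documents, and the 94.9% to 105.1% range rests on assumed rates of 0 to 5%. The primary estimate and its interval do not change.

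**What to change.** In SAP 9 and the main shells:

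1. Define the SVR12 non-response row as N minus SVR12 achievers.
2. State that the non-response categories apply only to those patients. Breakthrough and relapse among all eligible patients can still be reported as the separate secondary endpoints of Protocol 9.7.3.2.
3. Restore "missing SVR12 data and/or none of the above criteria" as the closing category of the main analysis and in shell 2.1.1.1.1. In shell 2.1.1.1.3, which omits missing results, add a row for patients who meet none of the listed criteria. The shells built by analogy, for the additional analysis and the other populations, should carry the same row.
4. Say whether a patient may appear in more than one category. Overlap is acceptable if stated, since both documents ask for each category as well as any.

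A single-category hierarchy and a sub-row for undetectable results with LLoD above 50 IU/mL are optional. The cost is a few lines of SAP text and a table row, with no new data.
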